**Inclusion Criteria**

- **Phase I:** Patients must have histologically confirmed relapsed or refractory non-

Hodgkin lymphoma or Hodgkin lymphoma (defined by WHO criteria), with no accepted curative options.

**Phase II:** Patients must have histologically confirmed T-cell lymphoma (as defined by WHO criteria), including central nervous system (CNS) involvement or lymphomatous meningitis.

**Exploratory Cohort:** Patients with histologically confirmed relapsed or refractory Germinal Center (GC)-derived B-Cell Lymphoma (diffuse large B-cell (DLBCL) and follicular lymphoma (FL)) defined by the WHO and Hans criteria with no accepted curative options. (Appendix 5)

- There is no upper limit for the number of prior therapies
- Evaluable Disease in the Phase I, and measurable disease as defined in Section 11.1 in the Phase II.
- Age  $\geq 18$  years.
- ECOG performance status  $\leq 2$
- Patients must have adequate organ and marrow function as defined in Section 3.1.6
- Adequate Contraception
- Ability to understand and the willingness to sign a written informed consent document.

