## 1.7 Exploratory Cohort Primary Objectives

- Determine the overall response rates (complete responses + partial responses) of oral azacitidine and romidepsin in patients with GC-derived B-cell lymphomas.
- Determine Progression Free Survival (PFS) and Time to Treatment Failure (TTF)
- Determine the Duration of Response (DOR)
- Determine the safety and tolerability of oral azacytadine and romidepsin in patients with relapsed or refractory GC-derived B-cell lymphoid malignancies.

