### 3. PATIENT SELECTION

#### 3.1 Inclusion Criteria for Lymphoma

**3.1.1** Phase I: Patients must have histologically confirmed relapsed or refractory non-Hodgkin lymphoma or Hodgkin lymphoma (WHO criteria), with no accepted curative options.

Phase II: Patients with untreated, relapsed or refractory T-cell lymphoma, including patients with central nervous system (CNS) involvement or lymphomatous meningitis are allowed on study.

**Exploratory Cohort:** Patients with histologically confirmed relapsed or refractory Germinal Center (GC)-derived B-Cell Lymphoma (diffuse large B-cell (DLBCL) and follicular lymphoma (FL)) defined by the WHO and Hans criteria with no accepted curative options. (Appendix 5)

**3.1.2.** There is no upper limit for the number of prior therapies. Patients may have relapsed after prior autologous or allogeneic stem cell transplant.

**3.1.3** Evaluable Disease in the Phase I, and measurable disease as defined in Section 11.1 for the Phase II.

**3.1.4** Age  $\geq 18$  years.

**3.1.5** ECOG performance status  $\leq 2$

**3.1.6** Patients must have adequate organ and marrow function as defined below:

- absolute neutrophil count  $\geq 1,000/\text{dL}$
- platelets  $\geq 75,000$  total ( $\geq 50,000$  if bone marrow involvement)
- bilirubin  $\leq 1.5X$  institutional limits
- AST(SGOT)/ALT(SGPT)  $\leq 2.0X$  institutional upper limit of normal
- Serum creatinine within normal institutional limits

OR

- Creatinine clearance  $\geq 50 \text{ mL/min}$  for patients with creatinine levels above institutional normal.

**3.1.7** Negative urine or serum pregnancy test for females of childbearing potential

**3.1.8** All females of childbearing potential must use an effective barrier method of contraception (either an IUDC or double barrier method using condoms or a diaphragm plus spermicide) during the

treatment period and for at least 1 month thereafter. Male subjects should use a barrier method of contraception during the treatment period and for at least 3 months thereafter. Female subjects should avoid the use of estrogen-containing contraceptives, since Romidepsin may reduce the effectiveness of estrogen-containing contraceptives.

**3.1.9** Ability to understand and the willingness to sign a written informed consent document.

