### **4.2 Screening**

All potential study patients will be screened and eligibility determined prior to enrollment. Unless otherwise specified, the following procedures and evaluations will be performed as noted in the study calendar (Section 10) prior to the start of study drugs (cycle 1, dose 1):

- 1) Obtain written informed consent and privacy authorization prior to initiating any protocol-required procedure that is not considered standard of care (See Section 4.3)

- 2) Review eligibility criteria
- 3) Review medical chart for past medical/surgical history
- 4) Record medications and prior treatment regiments
- 5) Record response to prior treatment regimen(s)
- 6) Document histopathology from:
  - (i) Original diagnosis
  - (ii) Tumor biopsy in the relapsed setting (if applicable)
- 7) Documentation of known measurable disease parameters by the following procedures:
  - CT of neck, chest, abdomen, and pelvis (PET/CT optional)
  - Skin exam
  - Other imaging techniques documenting disease site other than neck, chest, abdomen, and pelvis, if applicable
- 8) Obtain a 12-lead electrocardiogram (ECG) and calculate the QTc interval.
- 9) Perform a comprehensive physical examination
- 10) Assess and record ECOG Performance Status
- 11) Local laboratory: Collect blood for hematology (CBC with differential counts), chemistry (Na, K, Cl, HCO3, BUN, creatinine, glucose, calcium, magnesium, including serum  $\beta$ -human chorionic gonadotropin [ $\beta$ -hCG] pregnancy test for women who are not postmenopausal or surgically sterile [within 7 days prior to cycle 1, dose 1 and again within 24 hours prior to first dose of the study drugs.]), liver function tests (total protein, Albumin, AST, ALT, total bilirubin, direct bilirubin, alkaline phosphate).
- 12) Calculate creatinine clearance using the glomerular filtration rate (GFR) according to the Cockcroft and Gault Equation, only if screening serum creatinine is > 1.5 mg/dL:  $GFR^* = (140 - \text{age [years]}) \times \text{actual body weight (kg)} / 72 \times \text{serum creatinine}$   
 \*For female patients, multiply by 0.85
- 13) For Exploratory Cohort Only: A lymph node, core-needle biopsy, or bone marrow biopsy will be performed during the screening period for evaluation of gene expression profiling .

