**Table 10 : Response Criteria for NHL**

Response	Definition	Nodal Masses	Spleen/Liver	Bone Marrow CR
CR	Disappearance of all evidence of disease	a) FDG-avid or PET positive prior to therapy; mass of any size permitted if PET negative (b) Variably FDG-avid or PET negative; regression to normal size on CT	Not palpable, nodules disappeared	Infiltrate cleared on repeat biopsy; if indeterminate by morphology, immunohistochemistry should be negative
PR	Regression of measurable disease and no new sites	50% decrease in SPD of up to 6 largest dominant masses; no increase in size of other nodes	50% decrease in SPD of nodules (for single nodule in	Irrelevant if positive prior to therapy; cell type should be specified

		(a) FDG-avid or PET positive prior to therapy; one or more PET positive at previously involved site (b) Variably FDG-avid or PET negative; regression on CT	greatest transverse diameter); no increase in size of liver or spleen	
SD	Failure to attain CR/PR or PD	(a) FDG-avid or PET positive prior to therapy; PET positive at prior sites of disease and no new sites on CT or PET (b) Variably FDG-avid or PET negative; no change in size of previous lesions on CT		
Relapsed or PD	Any new lesion or increase by 50% of previously involved sites from nadir	Appearance of a new lesion(s) 1.5 cm in any axis, 50% increase in SPD of more than one node, or 50% increase in longest diameter of a previously identified node 1 cm in short axis Lesions PET positive if FDG-avid lymphoma or PET positive prior to therapy	50% increase from nadir in the SPD of any previous lesions	New or recurrent involvement

Abbreviations: CR, complete remission; FDG, [18F]fluorodeoxyglucose; PET, positron emission tomography; CT, computed tomography; PR, partial remission; SPD, sum of the product of the diameters; SD, stable disease; PD, progressive disease.

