### 11.2.3

#### Response Definitions

Complete Response (CR): Disappearance of all non-target lesions by PET/CT

Incomplete Response/Stable Disease (SD): Persistence of one or more non-target lesion(s) and/or maintenance of tumor marker level above the normal limits

Progressive Disease (PD): Appearance of one or more new lesions and/or unequivocal progression of existing non-target lesions

Although a clear progression of “non-target” lesions only is exceptional, the opinion of the treating physician should prevail in such circumstances, and the progression status should be confirmed at a later time by the review panel (or Principal Investigator).

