### ***Exploratory Cohort***

A total of 10 patients with GC-derived lymphoma will be accrued.

We estimate an average accrual of 1-2 patients per month, with a goal of completing accrual within 12 months.

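### The measurable-disease criterion in 3.1.3 omits the B-cell Exploratory Cohort, so patients who can be scored CR but not PR may enter a 10-patient group whose first primary objective is ORR

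*Combined protocol and SAP*

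**What the plan says.** Section 3.1.1 lists three populations with separate entry lines: Phase I, Phase II and the Exploratory Cohort. The cohort's line begins "Patients with histologically confirmed relapsed or refractory Germinal Center (GC)-derived B-Cell Lymphoma" and sets no condition on disease extent. Section 3.1.3 then reads "Evaluable Disease in the Phase I, and measurable disease as defined in Section 11.1 for the Phase II". The synopsis repeats it: "Evaluable Disease in the Phase I, and measurable disease as defined in Section 11.1 in the Phase II". The cohort appears in neither.

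Section 1.7 gives the cohort's first primary objective: "Determine the overall response rates (complete responses + partial responses) of oral azacitidine and romidepsin in patients with GC-derived B-cell lymphomas". Duration of response is another primary objective there. Section 13.2 fixes the size: "A total of 10 patients with GC-derived lymphoma will be accrued". Section 13.3, under a heading that covers both Phase II and the cohort, calls for an ORR estimate with an exact 95% interval.

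Table 10 defines PR as "Regression of measurable disease and no new sites", quantified by a 50% fall in the sum of products of diameters. For non-target lesions, Section 11.2.3 offers only CR, SD and PD. Its middle category is "Incomplete Response/Stable Disease (SD): Persistence of one or more non-target lesion(s) and/or maintenance of tumor marker level above the normal limits".

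**The concern.** The cohort's main result is a response rate, and half of the definition of response (PR) depends on having something measurable. Phase II, which has the same endpoint, is protected by 3.1.3; the cohort is not. A patient whose only disease is non-measurable under Section 11.1.2 (for example lesions under 10 mm on spiral CT, bone lesions or effusions) meets the entry criteria as written. If that patient improves substantially without clearing all disease, the protocol has no category for it other than SD.

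With 10 patients, each one is worth 10 percentage points of the observed ORR. Keeping such patients in the denominator pulls the estimate down. Removing them afterwards shrinks an already small sample and is a post hoc choice. A PR that cannot be scored also contributes no duration of response.

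**Working it through.** The plan gives no derivation for the cohort's 10 patients, so there is no figure to reproduce. The check has two parts.

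**Does any other text close the gap?**

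- *Cohort read as part of Phase II.* The synopsis (target population, sample size) and Sections 3.1.1, 13.1 and 13.2 list the two separately. Where a rule covers both, the heading says so: the synopsis treatment plan, the schema and Section 13.3. Section 3.1.3 does not.
- *Screening item 7 (Section 4.2).* It asks for known measurable disease to be documented, but as a procedure and not as a condition of entry.
- *Response-evaluable definition (Section 11.1.1).* It needs one day of therapy and a re-evaluation of disease. It has no measurability condition, so these patients stay in the denominator.
- *Opening of Section 11.1.* It assigns measurable disease to Phase I and evaluable disease to Phase II, the reverse of 3.1.3, and it too is silent on the cohort.

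No passage closes the gap.

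**How large could the effect be?** Let *k* be the number of the 10 patients without measurable disease, *R* the true ORR, and *c* the share of responses that are CR. The documents give none of these for the cohort, so all three are assumed. Patients with measurable disease are scored fully; the others can contribute only CRs:

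expected ORR = [(10 − k)·R + k·R·c] / 10 = R·[1 − k(1 − c)/10]

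For R = 50%:

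| k | c = 0.5 | c = 0 (worst case) |
|---|---|---|
| 1 | 0.5 × (1 − 0.05) = 47.5% | 0.5 × (1 − 0.10) = 45% |
| 2 | 0.5 × (1 − 0.10) = 45% | 0.5 × (1 − 0.20) = 40% |
| 3 | 0.5 × (1 − 0.15) = 42.5% | 0.5 × (1 − 0.30) = 35% |

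For R = 25% and c = 0, k = 1, 2, 3 gives 22.5%, 20% and 17.5%.

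*Duration of response.* The expected number of responders lost is k·R·(1 − c). With R = 50% and k = 3 this is 3 × 0.5 × 0.5 = 0.75 of an expected 5 responders if half of responses are CR, and 3 × 0.5 × 1 = 1.5 of 5 with no CRs.

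*Excluding such patients instead.* The Clopper-Pearson 95% interval is 18.7% to 81.3% for 5/10 (width 62.6 points), 15.7% to 84.3% for 4/8 (68.6 points) and 11.8% to 88.2% for 3/6 (76.4 points).

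*After the fix.* All 10 patients can be scored CR or PR, and the denominator stays 10.

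**The case against.** The strongest reply is that this is a small drafting slip in a cohort that Section 13.1 calls descriptive. It has no hypothesis, power or stopping rule, and worst-case expected shifts of 5 to 15 points are small beside an exact interval of about 19% to 81% at 5/10. The working expectation is plainly measurable, mostly nodal disease: the schema specifies a lymph node biopsy for this cohort, and screening item 7 documents measurable disease for everyone. All of that stands, and it limits the importance of the point. It does not supply the missing criterion, and in a descriptive cohort the estimate is the whole product.

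Three stronger readings are tempting, and the documents do not support them.

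- *A reader might infer that such patients can never be responders.* They can. Table 10 has a marrow criterion for CR, Section 11.2.3 allows CR for non-target disease, and the study calendar requires a repeat marrow biopsy where marrow was involved at baseline and imaging and examination show CR. Only PR is out of reach, so the loss of responders for duration of response is also partial.
- *A reader might infer that a cohort patient needs neither measurable nor evaluable disease.* Section 9.2.1 makes a biopsy confirming recurrent or refractory disease mandatory, and Section 11.1.2 classes every non-measurable site as evaluable. Only the measurable threshold is open.
- *A reader might take screening item 13 as a sign that marrow-only patients are expected.* It says "A lymph node, core-needle biopsy, or bone marrow biopsy will be performed during the screening period for evaluation of gene expression profiling". That lists acceptable tissue sources; a patient biopsied in the marrow may also have measurable nodes.

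**Conclusion.** The gap is real but modest. As written, patients with only non-measurable disease can enter the cohort, remain evaluable for response and have no route to PR. The direction of the bias in ORR is downward. Its size rests on assumptions: with a true ORR of 50% and 1 to 3 such patients among 10, the expected loss is 2.5 to 7.5 points if half of responses are CR, and 5 to 15 points if none are. If no such patient enrols, there is no loss. Nothing in the documents indicates how many would.

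The consequence is confined to the cohort's descriptive ORR, its interval and its duration of response. No type I error rate, power or go/no-go rule changes, and the Phase II two-stage test is not touched by this omission.

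**What to change.** In 3.1.3 and the matching synopsis line, extend the measurable-disease requirement so that it names the Exploratory Cohort alongside Phase II, keeping the reference to Section 11.1.

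In the same amendment, reconcile the opening of Section 11.1 with 3.1.3 and name the cohort there. Otherwise the amended criterion would point to a section that contradicts it for both phases and does not mention the cohort.

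The cost is a few words of text. The sample size stays at 10. The one real downside is that a patient without measurable disease, such as one with marrow involvement only, would not be eligible for the cohort.

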## **3.2 Exclusion Criteria**

**3.2.1** Prior Therapy

- ❖ Exposure to chemotherapy or radiotherapy within 2 weeks prior to entering the study or those who have not recovered from adverse events due to agents administered more than 2 weeks earlier.
- ❖ Systemic steroids that have not been stabilized ( $\geq 5$  days) to the equivalent of  $\leq 10$  mg/day prednisone prior to the start of the study drugs.
- ❖ No other concurrent investigational agents are allowed.

**3.2.3** History of allergic reactions to Oral 5-azacitidine or Romidepsin.

**3.2.4** Uncontrolled intercurrent illness including, but not limited to, ongoing or active infection, symptomatic congestive heart failure, unstable angina pectoris, cardiac arrhythmia, or psychiatric illness/social situations that would limit compliance with study requirements.

**3.2.5** Pregnant women

**3.2.6** Nursing women

**3.2.7** Active concurrent malignancy (except non-melanoma skin cancer or carcinoma *in situ* of the cervix). Patients whose lymphoma has transformed from a less aggressive histology remain eligible.

**3.2.8** Patients known to be Human Immunodeficiency Virus (HIV)-positive

**3.2.9** Patients with active hepatitis A, hepatitis B, or hepatitis C infection.

**3.2.10** Concomitant use of CYP3A4 inhibitors (see Appendix 2)

**3.2.11** Any known cardiac abnormalities such as:

- Congenital long QT syndrome
- QTc interval  $\geq 500$  milliseconds;
- Patients taking drugs leading to significant QT prolongation (See Appendix 1: Medications That May Cause QTc Prolongation)
- Myocardial infarction within 6 months of C1D1. [Subjects with a history of myocardial infarction between 6 and 12 months prior to C1D1 who are asymptomatic and have had a negative cardiac

risk assessment (treadmill stress test, nuclear medicine stress test, or stress echocardiogram) since the event, may participate];

- Other significant ECG abnormalities including 2nd degree atrio-ventricular (AV) block type II, 3rd degree AV block, or bradycardia (ventricular rate less than 50 beats/min);
- Symptomatic coronary artery disease (CAD), *e.g.*, angina Canadian Class II-IV (see Appendix 3) In any patient in whom there is doubt, the patient should have a stress imaging study and, if abnormal, angiography to define whether or not CAD is present;

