### 5.1.2 Regimen Description (Phase 2)

Treatment will be administered on an outpatient basis. Patients will be treated with oral 5-azacytidine and romidepsin at the MTD (i.e the Recommended Phase 2 Dose, or RP2D). The treatment will be administered as follows: oral 5-azacytidine 300 mg (flat dose) Days 1-14 and romidepsin 14 mg/m^2 on Days 8, 15, and 22 on an every 35 day cycle. All patients receiving romidepsin will receive potassium and magnesium supplementation as recommended in the package insert of the product. In all cycles romidepsin will be administered first over 4 hours. Reported adverse events and potential risks for oral 5-azacitidine and romidepsin are described in Section 7. Appropriate dose modifications are described in Section 6. No investigational or commercial agents or therapies other than those described may be administered with the intent to treat the patient's malignancy.

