### 5.1.3

#### Required Blood Parameters and Other Investigations Prior to Each Treatment (Except Cycle 1 Day 1)

Before the start of each treatment, patients should be reassessed and the following criteria must be fulfilled:

- ANC > 1000/dL
- Platelet count  $\geq$  50, 000/dL
- Serum creatinine concentration  $\leq 2.0 \times$  ULN or  $\leq$  baseline, or creatinine clearance  $> 50$  ml/min
- AST (SGOT) and ALT (SGPT)  $\leq 2.0 \times$  ULN or  $\leq 3.0 \times$  ULN in presence of demonstrable liver metastases
- Bilirubin concentration  $\leq 2.0 \times$  ULN
- Serum potassium is  $\geq$  institutional LLN and magnesium is  $\geq$  laboratory LLN (supplements must be given to patients whose potassium is < laboratory LLN and/or whose magnesium is < laboratory LLN and serum electrolytes must be rechecked prior to romidepsin administration).
- Recovery of any drug-related non-hematological toxicity to Grade 1 or less, unless otherwise indicated

- ECG schedule as specified in Section 5.1.8.2.

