**TABLE 8: Dose Modifications for Romidepsin**

Dose Modifications for Romidepsin	
CTCAE Grade or Abnormal Value	Romidepsin
Thrombocytopenia	
Grade 1 ( $75 \times 10^9/L - < LLN$ ) Grade 2 ( $50 - < 75 \times 10^9/L$ )	Maintain dose level Maintain dose level
Grade 3 or 4 thrombocytopenia:  OR  Thrombocytopenia that requires platelet transfusion or recurrent Grade 3 or 4 thrombocytopenia	Hold subsequent doses of therapy until thrombocytopenia returns to $\leq$ Grade 2 or baseline and continue at full dose  Hold subsequent doses of therapy until thrombocytopenia returns to $\leq$ Grade 2 or baseline and permanently reduce dose of romidepsin to the next reduced level below.. If the same toxicity recurs despite dose reduction, patients should be taken off study.
Neutropenia (ANC)	
Grade 1 ( $1.5 \times 10^9/L - < LLN$ ) Grade 2 ( $1.0 - < 1.5 \times 10^9/L$ )	Maintain dose level Maintain dose level
Grade 3 and 4 neutropenia:	Hold subsequent doses of therapy until specific cytopenia returns to $\leq$ Grade 1 or baseline and continue at full dose
Febrile Neutropenia	
Febrile ( $\geq 38.5^{\circ}C$ ) Grade 4 neutropenia or recurrent Grade 3 or 4 neutropenia:	Hold subsequent doses of therapy until neutropenia returns to $\leq$ Grade 1 or baseline and permanently reduce dose of romidepsin to the next reduced level below.. If the same toxicity recurs despite dose reduction, patients should be taken off study
All Other Non-Hematologic Drug Toxicities (not mentioned in previous tables)	
Grade 1 or 2:	Maintain dose level
Grade 3	Hold treatment with romidepsin until toxicity returns to $\leq$ Grade 1 or baseline, then restart therapy at full dose. If Grade 3 toxicity recurs, reduce dose of romidepsin to the next reduced level below.. This is a permanent dose reduction.
Grade 4	Grade 4 toxicity: Hold treatment with romidepsin until toxicity returns to $\leq$ Grade 1 or baseline, and then restart therapy at the next reduced level below.. This is a permanent dose reduction

Dose interruption or study discontinuation is not required for lymphopenia of any grade.

In general, if study drug has been held and the toxicity does not resolve, as defined above, then drug must

be discontinued.

Note: Dose reductions should not be performed for alopecia or for nausea or vomiting that was not treated with aggressive anti-emetic support.

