## 10. STUDY CALENDAR

Baseline evaluations are to be conducted as indicated in the table below, prior to start of protocol therapy. Scans must be done  $\leq$ 4 weeks prior to the start of therapy. In the event that the patient's condition is deteriorating, laboratory evaluations should be repeated within 48 hours prior to initiation of the next

cycle of therapy.

Cycle	Screening	1				2- onward				End of treatment	End of Study (4 weeks after last dose)	Follow-up j
		Day 1	Day 8	Day 15	Day 22	Day 1	Day 8	Day 15	Day 22			
Eligibility & Safety Monitoring												
Informed Consent	X c											
Demographics	X c											
Medical History	X c											
Concurrent Medications	X f	X g	X	X	X	X	X	X	X	X	X	X
Physical exam	X f	X g	X	X	X	X				X	X	X
Vital Signs, weight	X f	X	X	X	X	X				X	X	X
Performance Status	X f	X	X	X	X	X				X	X	X
CBC w/ differential	X f	X g	X	X	X	X	X	X	X	X	X	X
Chemistries a, i	X f	X g				X				X	X	X
EKG	X c		X				X			X	X	
Toxicity Assessment			X	X	X	X				X	X	X
Serum β-hCG	X f											
Urinalysis	X c	X g										
Creatinine clearance	X											
Drug Dispensation												
Oral 5-azacitidine		X				X						
Romidepsin			X	X	X		X	X	X			
Efficacy Measurements												
CT (PET/CT optional)	X c						X b					
Brain MRI	X c, l											
Bone Marrow Biopsy k	X									X c		
Lymph Node Assessment	X c											
PK/Biomarkers												
Lymph Node Biopsy, FNA, or Bone Marrow Biopsy (Optional)	X c		X l									
PK		X d	X d			X						
Correlative Blood Sample		X h										

a) Chemistries include: Chem \*, Mg+, K+, Creatinine, Hepatic Function Panel (LFTs, bilirubin), and LDH. On romidepsin days of cycles 2 and onward, full chemistries may be drawn, but only K+ and Mg+ are required.  
b) CT to occur after cycle 2 and 6, Then CT q3-6 months, until disease progression or initiation of new therapy at the discretion of the Investigator. (PET/CT is optional)  
c) Bone Marrow biopsy will be required after cycle 2 for patients with bone marrow involvement at baseline who have a complete response by imaging and physical exam  

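### Marrow limits in Sections 3.1.6 and 5.1.3 are written per dL, 100,000-fold below Table 8; per µL is evidently meant, and the entry platelet limit has no volume unit

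*Combined protocol and SAP*

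**What the plan says.** **Entry.** Section 3.1.6 requires "absolute neutrophil count $\geq 1,000/\text{dL" and "platelets $\geq 75,000$ total", with a lower platelet limit of 50,000 when the marrow is involved. The neutrophil limit is per dL. The platelet limit has no volume unit.

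**Re-treatment.** Section 5.1.3 requires neutrophils above 1,000 per dL and platelets of at least 50,000 per dL. Its heading limits these checks to blood parameters "Prior to Each Treatment (Except Cycle 1 Day 1"), so they do not govern the first dose.

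**Reference unit.** Table 8 in Section 6.3.1 (romidepsin dose modifications, not the reporting-exclusions table in Section 7.4.2 that is also numbered 8) works in 10⁹/L. Grade 2 neutropenia runs from 1.0 to below 1.5, and Grade 2 thrombocytopenia from 50 to below 75. The dose is maintained in these bands and held below them.

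**Population and start of dosing.** Section 3.1.1 opens Phase II to "Patients with untreated, relapsed or refractory T-cell lymphoma". Section 5.1.2 gives "oral 5-azacytidine 300 mg (flat dose) Days 1-14", so azacitidine starts a week before the first romidepsin infusion on Day 8.

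**The concern.** These are operative thresholds. They decide who may enter and who may be re-dosed on a myelosuppressive combination. Section 2.4.2 reports Grade 3/4 febrile neutropenia and Grade 3/4 thrombocytopenia, each in 19.2% of Phase I patients, and the two events that set the maximum administered dose were Grade 4 cytopenias. A limit that screens out nobody as written cannot be enforced or audited, however obvious the intention.

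The exposure is greatest at entry. Because Section 5.1.3 exempts Cycle 1 Day 1, Section 3.1.6 is the only numeric count limit before azacitidine begins. Exclusion 3.2.1 helps in part, since it bars "those who have not recovered from adverse events due to agents administered more than 2 weeks earlier". It does not reach low counts caused by the lymphoma itself, and the trial admits untreated patients and patients with marrow involvement.

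**Working it through.** No sample size, power or alpha figure depends on these limits, so there is no design figure to reproduce. The check is a unit conversion against Table 8.

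**Conversion.** 1 L = 10 dL = 10⁶ µL, so 1 dL = 100,000 µL.

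| Limit | As written | Converted | Table 8 cut-point | Ratio |
|---|---|---|---|---|
| Entry neutrophils (3.1.6) | 1,000/dL | 1,000 × 10 = 10⁴/L = 0.00001 × 10⁹/L | 1.0 × 10⁹/L | 1.0 / 0.00001 = 100,000 |
| Re-treatment neutrophils (5.1.3) | 1,000/dL | 0.00001 × 10⁹/L | 1.0 × 10⁹/L | 100,000 |
| Re-treatment platelets (5.1.3) | 50,000/dL | 50,000 × 10 = 5 × 10⁵/L = 0.0005 × 10⁹/L | 50 × 10⁹/L | 50 / 0.0005 = 100,000 |

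Per µL, the written limits are 1,000 / 100,000 = 0.01 neutrophils and 50,000 / 100,000 = 0.5 platelets.

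**The same numbers read per µL.**
- 1,000 × 10⁶ = 1.0 × 10⁹/L, the lower bound of Grade 2 neutropenia.
- 50,000 × 10⁶ = 50 × 10⁹/L, the lower bound of Grade 2 thrombocytopenia.
- 75,000 × 10⁶ = 75 × 10⁹/L, the boundary between Grades 1 and 2 thrombocytopenia.

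All three land exactly on a Table 8 boundary, which identifies the intended unit.

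**Illustration at entry (hypothetical patient).** Take an untreated patient with marrow disease and neutrophils of 0.8 × 10⁹/L, that is 800/µL. Per dL this is 800 × 100,000 = 80,000,000. The patient meets Section 3.1.6 as written and fails the intended 1,000/µL.

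The Section 10 calendar lists "CBC w/ differential" on Day 1 and Day 8 of Cycle 1. No numeric dosing rule attaches to the Day 1 count; Day 8 is the first with one. Azacitidine due on Days 1 to 7 is 7 × 300 = 2,100 mg, out of 14 × 300 = 4,200 mg for the cycle, or 50%.

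**Rules that act once treatment has started.**
- For Grade 3 and 4 neutropenia, Table 8 says "Hold subsequent doses of therapy until specific cytopenia returns to" Grade 1 or less, or baseline. The thrombocytopenia rows hold in a similar way.
- Section 6.1 holds both drugs for dose-limiting toxicity.
- Section 6.2 lets treatment resume after neutropenia only at Grade 2 or below.
- Section 5.2 also counts as dose-limiting a toxicity that delays Cycle 2.
- Section 7.2.1.1 describes postponing azacitidine in the following cycle as usual management of cytopenia.

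These cover most of what a faulty Section 5.1.3 leaves open. They do not supply an entry limit.

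**The case against.** The strongest reply is that this is a typing error nobody would act on. Section 3.1.6 opens by requiring adequate marrow function, the platelet figures beside the neutrophil limit make sense only per µL, and Table 8 gives the same boundaries in a correct unit. Under Section 4.4 the study coordinator verifies eligibility against laboratory copies and confirms registration with the principal investigator. The 100,000-fold factor then measures the slip, not a change in who is treated. This stands, and it is why the point is small. It does not make the written thresholds correct.

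Second, in machine-read PDF text a micro sign can come out as a d. This cannot be excluded without the source page. It is less likely because the same unit appears three times in two sections, and Greek letters survive elsewhere (β-hCG in Section 4.2, α1-acid-glycoprotein in Section 2.3.3). The missing platelet unit does not depend on it.

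Third, the 2,100 mg figure is not a bound on exposure. Table 8 allows treatment once counts are back to baseline, and a patient who enters at 0.8 × 10⁹/L is already at baseline on Day 8. This is right: the figure only counts doses scheduled before the Day 8 check.

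Finally, Table 8 and Section 6.2 set different restart levels for neutropenia, and correcting the unit will not reconcile them. That is true, but it is a separate matter.

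**Conclusion.** The point holds. Taking the text as it reads, three operative limits are 100,000-fold below the plan's own cut-points, and a fourth, entry platelets, has no volume unit. The intended values can be recovered from Table 8 without new clinical judgement.

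The correction is minor but should be made, because these are safety thresholds. The residual gap is mainly at entry, for patients whose low counts come from the lymphoma and not from earlier treatment. No demonstrated harm is claimed: nothing in the documents shows a patient enrolled or dosed on the literal reading. Sample size, alpha and the response-rate analysis do not change.

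The neutrophil and re-treatment platelet part assumes that the source page does read dL. The missing entry platelet unit stands either way.

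**What to change.** 1. Check the source page for a misread micro sign.
2. If it reads dL, amend Section 3.1.6 to entry neutrophils ≥ 1,000/µL, and Section 5.1.3 to neutrophils > 1,000/µL and platelets ≥ 50,000/µL.
3. In either case, state the entry platelet limit in Section 3.1.6 as ≥ 75,000/µL, or ≥ 50,000/µL with marrow involvement.
4. Bring the eligibility screening worksheet in Section 4.4 into line.

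The cost is a wording amendment and a worksheet update, with no added patients, visits or procedures.
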